10.1.3 Exploratory Endpoints

To describe pharmacodynamic effects, serial measures of megakaryocytes and other hematopoietic cells will be summarized using descriptive statistics such as means, medians and ranges for each time point. These measures will be plotted

for each patient, and these patient specific plots will be plotted for all patients together. Analyses for change over time will be done using repeated measures general linear model analysis.

To evaluate the relationship between biomarker expression levels and response, changes in biomarker expression levels will be related to response using a Wilcoxon rank sum test. To evaluate reduction in splenomegaly by palpation in the MF arm, a categorical variable measuring the extent of splenomegaly will be tracked over time descriptively, since the small sample size will preclude longitudinal analysis. To evaluate improvement in MF symptoms in the MF arm, the Myeloproliferative Neoplasm Symptom Assessment (MPN-SAF) score will be summarized descriptively over time using means, medians, standard errors and ranges.

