4.3 Dose Modifications & Delays

Any patient who receives at least one dose of study therapy will be evaluable for toxicity endpoints. Each patient will be assessed for the development of toxicity according to the timeframe referenced in Section 5). Toxicity will be evaluated according to the NCI's CTCAE v 4. To manage excessive toxicity, reduction of the total alisertib dose can be done by reducing the daily dose administered and/or by interruption of the schedule treatment within a cycle.

In general treatment delays of up to 1 week for any reason are permitted. If a patient fails to meet the above-cited criteria for a new cycle of therapy, then initiation of the next cycle *should be delayed* for up to 1 week. At the end of that week, the patient should be re-evaluated to determine whether the criteria for retreatment have been met. Should treatment need to be delayed for more than 1 week because of incomplete recovery from treatment-related toxicity, the dose of alisertib will be reduced (see table below) to 40 mg BID when therapy resumes. A second dose reduction to 30 mg BID may occur should treatment need to be delayed for more than 1 week because of incomplete recovery from treatment-related toxicity at the 40 mg BID dose. Patients who require further dose reduction will be removed from the study. Should treatment need to be delayed for more than 2 weeks at any dose, therapy with alisertib will be discontinued.

Dose Level	Alisertib¹
Level 1 (starting dose)	50 mg
Level -1	40 mg
Level -2	30 mg
Level -3	Discontinue

¹ Doses are administered orally, BID on days 1-7 of each cycle.

4.3.1 **Dose Modifications for Hematological Toxicities**

If a patient experiences any of the following hematological toxicities during the dosing period, dosing will be discontinued for the remainder of that cycle and the dose will be decreased by 1 level (-10 mg) for all subsequent cycles of treatment.

- Grade 4 neutropenia (ANC < 500 cells/mm³) lasting more than 7 consecutive days
- Grade 4 thrombocytopenia (platelet count < 25,000/ μ L) lasting more than 7 consecutive days
- Platelet count less than 10,000/ μ L at any time
- Grade 3 neutropenia with fever or infection, or both, where fever is defined as an oral temperature greater than 38.5°C
- Grade 3 thrombocytopenia with clinically significant bleeding

4.3.2 **Dose Modifications for Non-hematological Toxicities**

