4.6 Duration of Therapy

Patients may continue to receive alisertib treatment until any of the following occur:

- Disease progression
- Development of an inter-current illness that prevents further administration of treatment
- Unacceptable adverse event(s)
- Patient decides to withdraw from either study treatment or the as a whole study
- The treating investigator determines that the patient should be taken off treatment for any reason (i.e. changes in condition, inability to comply with study treatment or procedures)

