- ^g Disseminated intravascular coagulation (DIC) screen should include: PT/INR, aPTT, fibrinogen, and D-dimer. Cycle 1 day 1 PT/INR/aPTT does not need to be performed if the screening DIC was within 3 days of this visit. If the initial DIC is positive follow-up coagulation studies should include the full DIC panel (rather than the PT/INR/aPTT alone). See footnote t.
Note: Beyond Cycle 6, PT/INR, aPTT testing is not required.
- ^h Serum pregnancy test required for women of child-bearing potential during screening AND pre-dose on Cycle 1 day 1. Results must be available and negative prior to dosing. See footnote t.
- ⁱ It is strongly preferred that correlative samples be collected and shipped only on Monday – Thursday (with same day shipment preferred). Friday collections/shipments should be avoided to ensure sample stability. Since these samples are collected on Day 1 of each cycle, it is preferred that Day 1 visits be conducted on Monday through Thursday when correlative samples are being collected. Sites should use the available windows to achieve this. Please contact the QAM if there are any questions
- ^j Peripheral blood (25 ml) and/or bone marrow (bone marrow only if done clinically – will collect about 10-20 ml) samples will be collected for determination of alisertib pharmacodynamics (PD studies). Blood samples will be collected at the start of each cycle (D1). Sample collection at D15 will be optional. (Samples will be collected for a maximum of 6 cycles). Correlative bone marrow samples should be obtained any time bone marrows are collected as clinically indicated during study participation. . At baseline, correlative bone marrow collection is not mandatory for study entry. However, study team should request 3-4 unstained slides from any prior bone marrow testing performed within the last year before study entry. Please refer to laboratory manual for details.
- ^k Bone marrow aspirate and biopsy is required within 1 year prior to registration (provided the PI confirms the diagnosis and there is no suspicion for acceleration to blast phase), on C7D1 (+/-14 days) and thereafter only as clinically indicated.
- ^l Palpation for splenomegaly and MPN-SAF will be done only on MF patients. Baseline MPN-SAF and palpation for Splenomegaly within 14 days of registration

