- ^h Serum pregnancy test required for women of child-bearing potential during screening AND pre-dose on Cycle 1 day 1. Results must be available and negative prior to dosing. See footnote s.
- ⁱ It is strongly preferred that correlative samples be collected and shipped only on Monday – Thursday (with same day shipment preferred). Friday collections/shipments should be avoided to ensure sample stability. Since these samples are collected on Day 1 of each cycle, it is preferred that Day 1 visits be conducted on Monday through Thursday when correlative samples are being collected. Sites should use the available windows to achieve this. Please contact the QAM if there are any questions.
- ^j Peripheral blood (25 ml) and/or bone marrow (if done will collect about 10-20 ml) samples will be collected for determination of alisertib pharmacodynamics (PD studies). Samples will be collected at the start of each cycle(D1). Sample collection at D15 will be optional. Samples will be collected for a maximum of 6 cycles. Please refer to laboratory manual for details.
- ^k Bone marrow aspirate and biopsy will be performed at screening (within 21 days prior to registration), cycle 2 day 1, and after cycle 4 (between days 21 and 35). For patients not yet in CR after cycle 4, bone marrow aspirate and biopsy should be repeated after cycle 6 (between days 21 and 35). Thereafter bone marrows should be repeated as clinically indicated.
- ^l Labs and exam only required on day 1 of cycles 7 and beyond (although additional may be performed as clinically indicated).
- ^m Patients will be administered orally on days 1-7 of each cycle (1 cycle = 21 days); patients may remain on treatment until development of unacceptable toxicity or progression of disease.
- ⁿ Patients will have an end of treatment (EOT) visit approximately 30 days (+10 days) after the last dose of treatment; if a bone marrow was carried out at disease progression, this will be considered the EOT marrow and does not need to be repeated at the EOT visit.
- ^o Patients will have a final end of study (EOS) visit approximately 6 months (+/- 30 days) after the last dose of treatment to assess for late-onset toxicity.
- ^p Labs *required* only on days 1 and 15 of cycles 2-6, but in the event of cycle 1 toxicity or at treating investigator's discretion, additional interim labs may be performed per standard of care.
- ^q Baseline Medical History within 14 days of registration

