9.0 CORRELATIVE STUDIES

9.1 Sample Collection

Blood and/or bone marrow samples for PD studies will be collected at multiple timepoints for cycles 1-6. Samples will be collected at the time of routine blood and/or bone marrow collection on Day 1 of each cycle. Sample collection on Day 15 will be optional. For MF patients, only peripheral blood samples will be collected unless bone marrow is deemed medically necessary; AMKL patients may include both blood and bone marrow procurement. Approximately 25 ml of peripheral blood and 10-20 ml of bone marrow will be collected in lavender top EDTA tubes and dark green top tubes respectively, and labeled with the patient initials, study number, and date of collection. Samples may sit at room temperature until they are picked up or shipped.,.

As mentioned above, correlative bone marrow samples should be obtained any time bone marrows are collected as clinically indicated during study participation. At baseline, bone marrow collection is not required for study entry, but study team should request 3-4 unstained slides from prior bone marrow testing performed within the last year. Unstained slides should be shipped at room temperature to [name]

It is strongly preferred that correlative samples be collected and shipped only on Monday – Thursday (with same day shipment preferred). Friday collections/shipments should be avoided to ensure sample stability. Since these samples are collected on Day 1 of each cycle, it is preferred that Day 1 visits be conducted on Monday through Thursday when correlative samples are being collected. Sites should use the available windows to achieve this. Please contact the QAM if there are any questions.

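### The pharmacodynamic change-over-time model in Section 10.1.3 has no rule for incomplete sample series, and in its classical form would exclude every patient with a missing time point

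*Combined protocol and SAP*

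**What the plan says.** Section 10.1.3 gives two treatments of the serial pharmacodynamic measures. The first is descriptive: they are to be "summarized using descriptive statistics such as means, medians and ranges for each time point", and plotted for each patient and for all patients together. The second is a model: "Analyses for change over time will be done using repeated measures general linear model analysis". No estimator, covariance structure, set of time points or missing-data rule is given for it.

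The sampling rules are elsewhere:

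- Section 9.1 ties collection to Day 1 of each cycle and adds: "Sample collection on Day 15 will be optional". Footnote j of the MF schedule (Section 5.1) agrees: "Sample collection at D15 will be optional". Footnote j of the AMKL schedule (Section 5.2) says the same.
- The series has an upper limit: "Samples will be collected for a maximum of 6 cycles" (Section 5.2, footnote j; Section 5.1 has the same limit).
- No minimum number of cycles is set. Section 4.6 says: "Patients may continue to receive alisertib treatment until any of the following occur". It then lists progression, intercurrent illness, unacceptable adverse events, withdrawal and investigator decision. Section 4.3 adds: "Should treatment need to be delayed for more than 2 weeks at any dose, therapy with alisertib will be discontinued".

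Section 10.2 caps enrolment at 24 patients, with any split between MF and AMKL.

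**The concern.** A repeated-measures general linear model in its classical form takes one row per patient and one column per time point. A patient with one empty cell is left out altogether. The design makes empty cells likely. Half of the scheduled blood samples are optional, and blood sampling for this purpose is tied to treatment cycles 1 to 6, so a patient who leaves treatment early contributes no later samples.

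Two things are at stake. One is precision, because the number of patients analysed could fall well below the number treated. The other is selection. Patients with a full series are those who did not progress, did not stop for toxicity and did not withdraw before cycle 6. A time trend estimated in them alone describes that group and not all treated patients.

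**Working it through.** The plan states no sample size, power or significance level for this analysis, so there is no figure to reproduce. The check asks how many patients would have complete series if the classical form were used.

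**Inputs from the documents**
- N = 24 at most (Section 10.2).
- Six Day 1 blood samples, one per cycle for cycles 1 to 6 (Sections 5.1, 5.2 and 9.1).
- Six optional Day 15 blood samples, giving 12 points if all are taken.

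**Assumptions, because the documents give no figure**
- r, the proportion still on treatment through cycle 6: 0.3 to 0.8.
- u, the chance that each optional Day 15 sample is taken: 0.5 to 0.95, independent across visits.
- No Day 1 sample is missed while a patient is on treatment. This is favourable to the plan.

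**Formulas**
- Complete Day 1 series: N × r.
- Complete 12-point series: N × r × u^6.

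With 0.8^6 = 0.262 and 0.9^6 = 0.531, for N = 24:

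| r | Day 1 only, 24r | All 12 points, u = 0.8 | All 12 points, u = 0.9 |
|---|---|---|---|
| 0.3 | 7.2 | 1.9 | 3.8 |
| 0.5 | 12.0 | 3.1 | 6.4 |
| 0.8 | 19.2 | 5.0 | 10.2 |

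Over the full assumed range, the 12-point count runs from 24 × 0.3 × 0.5^6 = 0.1 to 24 × 0.8 × 0.95^6 = 14.1. It therefore depends heavily on the unknown Day 15 uptake.

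**Whether a 12-point model could be fitted.** Twelve time points give 11 within-patient contrasts. An unstructured multivariate test of change in one group needs at least 12 complete patients. With the number complete taken as binomial(24, r × u^6), the chance of 12 or more is 0.0015 at r = 0.8 and u = 0.8, and 0.29 at r = 0.8 and u = 0.9.

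**By disease.** If one disease contributes 12 patients and r = 0.5, then 12 × 0.5 = 6 have complete Day 1 series. With u = 0.8, 6 × 0.262 = 1.6 have all 12 points.

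**Comparison.** A likelihood-based mixed model on one-row-per-sample data uses every treated patient with at least one usable sample, up to 24.

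These counts concern blood. Marrow samples follow a different timetable and are not counted.

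**The case against.** The strongest reply is that the plan never says patients with incomplete series are dropped. That is correct. A reader might infer deletion from the name of the model, but deletion belongs to one way of fitting it. The wording does not exclude a likelihood fit that keeps everyone. What stands is that the wording does not specify such a fit either, and the classical reading is a natural one.

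Second, optional Day 15 samples cost patients only if Day 15 is modelled. A Day 1 model avoids that loss. This also stands, and it is why the two sets of counts are kept apart. Early exit from treatment affects both.

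Third, a reader might infer that the whole pharmacodynamic analysis would rest on a handful of patients. The documents do not support that. The summaries at each time point and the patient plots use every available sample, and the stated aim is to describe effects.

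Fourth, a reader might see a contradiction with the spleen endpoint, which the same section keeps descriptive "since the small sample size will preclude longitudinal analysis". That reading should be dropped. The spleen sentence concerns a categorical variable in the MF arm only, whereas the model is for serial cell measures with no arm restriction. The two samples could coincide if all 24 patients had MF, but treating two different kinds of variable differently is not inconsistent.

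Finally, a mixed model is not a cure for every form of dropout. It assumes that missingness depends only on observed data. If patients leave for reasons tied to unobserved pharmacodynamic values, bias remains.

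**Conclusion.** The point holds as a gap with a foreseeable consequence. Section 10.1.3 names a model whose classical form discards incomplete patients, and it says nothing about time points or missing samples in a design where incomplete series are expected. If that form were used, about 7 to 19 of 24 patients would enter a Day 1 analysis. About 2 to 5 would enter a 12-point analysis at 80% Day 15 uptake. Both ranges rest on assumed retention of 30% to 80% and on no missed Day 1 samples. The direction of selection, toward patients who stay on treatment, follows from the stopping rules; its size cannot be estimated from the documents.

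The consequence is minor. This is an exploratory endpoint in a descriptive pilot, and neither the primary safety analysis nor the secondary response analysis is affected.

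**What to change.** In Section 10.1.3, replace the model sentence with a linear mixed model fitted by likelihood to all available samples:

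- a random intercept for each patient;
- the baseline sample retained in the analysis;
- cycle as a fixed effect;
- disease as a covariate where both diseases are enrolled;
- Day 1 samples as the main series, with Day 15 samples analysed as supportive only;
- the missing-at-random assumption stated;
- the number of patients contributing reported at each time point, so that a reader can see how far the later cycles depend on those who stayed.

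The cost is a few lines of text and slightly more modelling work. No extra samples, visits or patients are needed, and standard software suffices. The wording should be settled before the pharmacodynamic results are seen, so that the handling of incomplete series is not chosen afterwards.

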2.3 Exploratory Objectives & Endpoints

Exploratory objectives will include the following:

- 2.3.1 Describe pharmacodynamics (PD) effects of alisertib in peripheral blood and/or bone marrow samples.

Serial blood and/or bone marrow samples will be collected at specific timepoints. Flow cytometry, colony forming assays, AURKA autophosphorylation assays, and in vitro cultures of patient specimens to assess the effect of MLN8237 on megakaryocytes and other hematopoietic cells will be measured.

- 2.3.2 Evaluate the relationship between biomarker expression levels and response to alisertib.

Changes in biomarker expression levels from baseline will be measured (using PD samples) to correlate with response to alisertib therapy. Biomarkers will include a) genes encoding key enzymes in Aurora kinase signaling, b) markers of cellular aneuploidy and apoptosis, and c) markers of megakaryocytic differentiation.

- 2.3.3 Evaluate reduction in splenomegaly by palpation (MF arm only).

Patients will be examined for splenomegaly by palpation once per cycle and change from baseline will be calculated over time.

- 2.3.4 Evaluate improvement in MF symptoms (MF arm only), as assessed by the Myeloproliferative Neoplasm Symptom Assessment form (MPN-SAF).

The MPN-SAF will be administered to patients in the MF arm only once per cycle. Changes in symptom scores over time will be calculated.

- 2.3.5 Assess change in bone marrow fibrosis in patients in the MF arm. Bone marrow will be assessed at screening and after cycle 6 in this population.

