9.3 Processing and Analysis

Upon receipt, monocuclear cells will be collected from the samples by Ficoll preparation. Aliquots of the cells will be used in the following ways:

1. To extract RNA for gene expression studies. We will determine the pathways that are up or down-regulated upon Alisertib treatment. We anticipate changes in cell cycle regulatory and megakaryocyte differentiation pathways.

2. To isolate proteins for analysis of levels of key factors, such as transcription factors, ribosome assembly proteins, and signaling molecules. We will use western blot assays to determine the changes that occur with Alisertib treatment.
3. To perform flow cytometry will be performed to analyze the state of maturation of the cells, including CD41, CD42 expression and DNA content. We will use FlowJo software to analyze the flow cytometry data to determine the levels of these differentiation parameter.
4. To perform flow cytometry to assess the state of signaling cascades, such as the AKT, ERK, and STAT pathways. We will use FlowJo software to analyze the flow cytometry data to determine the levels of activation of these pathways.
5. To perform flow cytometry to assess the hematopoietic stem cell compartment. We will use FlowJo software to determine the different populations of hematopoietic stem and progenitor populations.
6. To culture in vitro and in vivo to assess the state and differentiation potential of hematopoietic progenitor cells.
7. We may elect to use samples at a later time point to directly compare differences in gene expression and signaling pathways from sequential patient specimens. Thus, we will freeze down aliquots of cells, and/or or RNA, and/or protein for future cell culture, flow cytometry, DNA, RNA and protein extractions. Samples will be kept for up to two years.
8. An optional correlative study (separate patient consent) will involve exome or whole genome sequencing on normal and tumor DNA for patients with AMKL. DNA from tumor samples will be available as in line 7 above; to obtain germline DNA, buccal swabs will be obtained.

Samples will be labeled with a number and not the patient names. Identifying information will be retained by the PI and co-investigators and not shared with the laboratory staff. Identities of the subjects will not be reported in presentations or publications.

Samples will be retained indefinitely in [name] laboratory located at Northwestern University.

Please refer to laboratory manual for more details.

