Appendix I – International Working Group Response Criteria for AML

Definitions of response criteria are based primary on those given by Cheson et al.

Category	Definition
Complete remission (CR) ¹	Bone marrow blasts <5 percent; absence of blasts with Auer rods; absence of extramedullary disease; absolute neutrophil count >1.0 x 10 ⁹ /L (1000/μL); platelet count >100 x 10 ⁹ /L (100,000/μL); independence of red cell transfusions
CR with incomplete recovery (CRi) ²	All CR criteria except for residual neutropenia (<1.0 x 10 ⁹ /L (1000/μL)) or thrombocytopenia (<100 x 10 ⁹ /L (100,000/μL))
Morphologic leukemia-free state ³	Bone marrow blasts <5%; absence of blasts with Auer rods; absence of extramedullary disease; no hematologic recovery required.
Partial remission (PR)	All hematologic criteria of CR; decrease of bone marrow blast percentage to 5 to 25%; and decrease of pretreatment bone marrow blast percentage by at least 50%.
Cytogenic CR (CRc) ⁴	Reversion to a normal karyotype at the time of morphologic CR (or CRi) in cases with an abnormal karyotype at the time of diagnosis; based on the evaluation of 20 metaphase cells from bone marrow.
Molecular CR (CRm) ⁵	No standard definition; depends on molecular target.
Treatment failure	
Resistant disease (RD)	Failure to achieve CR, CRi or PR; only includes patients surviving ≥7 days following completion of initial treatment, with evidence of persistent leukemia by blood and/or bone marrow examination.
Death in aplasia	Deaths occurring ≥ 7 days following completion of initial treatment while cytopenic; with an aplastic or hypoplastic bone marrow obtained within 7 days of death, without evidence of persistent leukemia.
Death from indeterminate cause	Deaths occurring before completion of therapy, or <7 days following its completion; or deaths occurring ≥7 days following completion of initial therapy with no blasts in the blood, but no bone marrow examination available.
Relapse ⁶	Bone marrow blasts ≥ 5%; or reappearance of blasts in the blood; or development of extramedullary disease.

¹ All criteria need to be fulfilled; marrow evaluation should be based on a count of 200 nucleated cells in an aspirate with spicules; if ambiguous, consider repeat exam after 5 to 7 days; flow cytometric evaluation may help to distinguish between persistent leukemia and regenerating normal marrow; a marrow biopsy should be performed in cases of dry tap, or if no spicules are obtained; no minimum duration of response required.

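### In AMKL, the planned link between RNA or protein biomarker change and response is confounded by the share of blasts in the sample, and can look positive with no change in expression per cell.

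*Combined protocol and SAP*

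**What the plan says.** Section 2.3.2 sets the exploratory objective: "Changes in biomarker expression levels from baseline will be measured (using PD samples) to correlate with response to alisertib therapy". It names three classes of marker: "genes encoding key enzymes in Aurora kinase signaling, b) markers of cellular aneuploidy and apoptosis, and c) markers of megakaryocytic differentiation".

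Section 9.3 describes the laboratory work. On receipt, "monocuclear cells will be collected from the samples by Ficoll preparation". Aliquots of those cells then go to several assays. One is "To extract RNA for gene expression studies", another is western blot of extracted protein, and another is flow cytometry "to analyze the state of maturation of the cells, including CD41, CD42 expression and DNA content". No sorting or blast enrichment precedes the RNA and protein steps.

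Section 10.1.3 gives the analysis in one sentence: "changes in biomarker expression levels will be related to response using a Wilcoxon rank sum test". It does not say which assay, which sample (blood or marrow) or which visit supplies the change, and it has no term for cell composition.

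Section 10.1.2 defines response as at least PR. For AMKL, Appendix I requires marrow blasts below 5% for CR. For PR it requires a fall to 5–25% together with a "decrease of pretreatment bone marrow blast percentage by at least 50" per cent. Both also require the CR blood-count criteria.

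**The concern.** A mononuclear-cell preparation from an AMKL patient mixes megakaryoblasts with other cells. RNA or protein extracted from it is an average weighted by the share of each. If a marker is expressed more, or less, in blasts than in the other cells, the average moves whenever the blast share moves. An AMKL responder must have lost marrow blasts, and a non-responder usually has not. The same quantity therefore drives the biomarker readout and helps define the comparison groups.

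The named markers are plausible candidates for such a difference. Section 1.2 describes AMKL blasts as hyperproliferative and failing to differentiate, and the markers cover Aurora signalling, ploidy and megakaryocytic differentiation.

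At stake is how objective 2.3.2 can be interpreted. Sections 1.2 and 1.6 present alisertib as a differentiation agent. A bulk association with response could be taken as patient-level support for that mechanism when it may only restate that blasts fell.

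**Working it through.** The plan states no alpha, effect size or sample size for this test, so there is no figure to reproduce. I assume a two-sided exact test at 0.05.

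**Inputs from the documents.** Response is at least PR (10.1.2) and the blast criteria are those of Appendix I. The trial takes at most 24 patients with no fixed AMKL number (10.2). The response rate is 10% in the precision statement (10.2) and 13% in the cited AML trial (1.6).

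**Assumed inputs.** The documents do not give the expression ratio r (blast to other cell), the blast shares in the PD sample, or the measurement noise. Ranges are shown.

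**Step 1: bulk level with constant expression per cell.** Bulk = f·r + (1 − f), where f is the blast share. For f falling from 0.40 to 0.05:

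| r | before | after | change |
|---|---|---|---|
| 2 | 1.40 | 1.05 | −25% |
| 4 | 2.20 | 1.15 | −48% |
| 10 | 4.60 | 1.45 | −68% |

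**Step 2: how often the test is positive with no per-cell change (12 AMKL patients, 3 responders).** Baseline blast share is uniform on 20–80%. Responders fall to 0–5%, or to 20–50% of baseline. Non-responders vary by ±30%. Noise SD is on the natural-log scale. At r = 1 the test is positive in about 4% of trials.

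| Setting | r = 2 | r = 4 | r = 10 |
|---|---|---|---|
| SD 0.2 | 39% | 83% | 97% |
| SD 0.5 | 10% | 30% | 59% |
| SD 0.2, blasts one fifth as frequent (e.g. blood) | 6% | 21% | 64% |
| SD 0.2, 2 of 9 non-responders also clear blasts | 19% | 30% | 38% |

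Two unfavourable assumptions together bring it closer to nominal. With SD 0.35 and one-fifth blasts the rates are about 5%, 10% and 31%.

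**Step 3: a second model.** Baseline share is 30–80%, responders end at no more than half of baseline and no more than 25%, non-responders vary by ±20%, and the log2 SD is 0.5. For 3 against 9 patients the rates are 3%, 18%, 53% and 78% at r = 1, 2, 4 and 8. At log2 SD 1.0 they are 4%, 7%, 19% and 34%. With the composition effect removed, as for a per-blast readout, the rate is about 3.5%.

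**Step 4: averaging over the number of responders.** The smallest two-sided p is 2/C(n,k) for k responders among n.
- n = 12: k = 1 gives 2/12 = 0.167 and k = 2 gives 2/66 = 0.030, so at least 2 responders are needed. That has probability 34% at a 10% response rate and 47% at 13%.
- n = 8: k = 3 gives 2/56 = 0.036, so at least 3 are needed.
- n = 6: the best case, k = 3, gives 2/20 = 0.10, so 0.05 cannot be reached.

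Under the second model with n = 12, r = 4 and log2 SD 0.5, the overall positive rate is 15% at a 10% response rate and 22% at 13%. At r = 1 it is 1–2%.

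**Step 5: what adjustment achieves.** In the Step 2 model (SD 0.2), response and blast change correlate at about −0.86. A linear adjustment for blast change leaves about 5%, 8% and 25% positive at r = 2, 4 and 10. That is much lower than without adjustment, but not clean at high ratios.

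**The case against.** **Circularity.** A reader might infer that the test is circular, so that responders differ from non-responders by construction. The documents do not support that. PR and CR also need neutrophil and platelet recovery and red-cell transfusion independence. Appendix I separately lists a morphologic leukemia-free state, in which blasts clear without recovery. Such patients weaken the link, as the last row of the Step 2 table shows.

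**Size.** A reader might also take the 39% to 97% row as the expected error rate. It is conditional on 3 responders among 12, which means at least 3 of 12 has probability only 11% at a 10% response rate and 20% at 13%. It also uses low noise and marrow-like blast shares. Section 9.1 allows blood or marrow for AMKL, and the AMKL number may be small or zero.

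**Flow cytometry.** Section 10.1.3 does not say that flow is left out. CD41, CD42 and DNA content match part of the marker list, and flow readouts analysed per cell are not affected in the same way. The laboratory manual, which is not among the documents, may add gating or enrichment.

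**Status.** The objective is exploratory, 10.1.2 calls the protocol purely descriptive, and no decision hangs on the test. Blast clearance may itself be a drug effect.

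All of this limits the size and scope. None of it removes the confounding for RNA and western-blot results as the protocol describes them, and a descriptive estimate or plot carries the bias just as a p-value does.

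**Conclusion.** The concern holds for RNA and western-blot biomarkers in AMKL, for markers expressed differently in blasts and other mononuclear cells. For these, the planned comparison cannot separate a change within cells from a change in the share of blasts.

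The size is uncertain. Changing one assumption at a time, the conditional false-positive rate with 3 responders among 12 runs from roughly 6% to 97%. The overall rate at a ratio of 4 is about 15–22% under the second model. Expression ratio, blast shares and noise are all assumptions, and the bias is weaker in blood with few blasts or before blasts have fallen. The documents do not support a claim that the test is positive by construction, that every listed biomarker is affected, or that a positive result shows no drug effect. What is missing is only the evidence for a change per cell.

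**What to change.** In 10.1.3:

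1. Analyse AMKL separately from MF, and state which assay, sample and visit supply the change. Choosing cycle 2 day 1 would not by itself put the marker before the response, because Section 5.2 footnote k schedules a marrow that day.
2. Report each RNA and protein change together with the blast fraction of the same sample from the planned flow cytometry. Show the unadjusted and the blast-fraction-adjusted change side by side. With few responders, a per-patient display is enough.
3. Define the blast fraction by a gate that does not rest on CD41 or CD42. These are differentiation readouts, and Section 1.2 reports that the screened compounds raise megakaryocyte surface markers, so adjusting for them could remove a real effect.
4. Analyse flow markers within the gated blast population.
5. State that an unadjusted bulk association alone will not be read as evidence of a per-cell mechanism.

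The cost is analysis wording and agreement with the laboratory on a gate. Flow is already planned on aliquots of the same cells, so no new visit or sample is needed. Section 9.3 names only CD41, CD42 and DNA content for the maturation panel, so the laboratory should confirm that a suitable blast gate is available. The downsides are that adjusted changes are imprecise, adjustment is incomplete with few responders (Step 5), and some samples will have few gated cells.
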